1. INTRODUCTION AND OBJECTIVES OF ANALYSIS

1.1. Introduction

This statistical analysis plan (SAP) is designed to outline the methods to be used in the analysis of study data to answer the study objective(s). Analysis sets, data handling rules, statistical methods, and formats for data presentation are provided. The statistical analyses and summary tabulations described in this SAP will provide the basis for the results sections of the clinical study report (CSR) for this trial.

1.2. Objectives

The primary objective is:

- To evaluate the safety and tolerability of a single injection of VAX-24 at three dose levels administered to healthy adults 65 years and older.

The secondary objective is:

- To assess the induction of antibody responses by VAX-24 dose levels compared to control groups receiving PCV20

2. STUDY DESIGN

2.1. Introduction

This Phase 2, randomized, observer-blind study is to be conducted in healthy adults aged 65 and older. Subjects may screen for up to 30 days prior to randomization; however, they may be screened and randomized within the same visit. Demographics, medical history, and concomitant medication use will be collected. Subjects will be randomly assigned in a 1:1:1:1 ratio to receive either VAX-24 at one of three dose levels or the active comparator, Prevnar 20 (PCV20).

Subjects will receive VAX-24 or PCV20 on Day 1. Solicited Adverse Events (AEs) will be collected for 7 days postvaccination via diary and unsolicited safety information for 28 days post-vaccination, with Serious Adverse Events (SAEs), new onset of chronic illnesses (NOCIs), and medically attended adverse events (MAAEs) collected up to 6 months post- vaccination. All subjects will have blood samples drawn for immunogenicity analysis for opsonophagocytic assay (OPA) and Immunoglobulin G (IgG) at Days 1 and 29. A Data Monitoring Committee (DMC) will be assembled for the study. If the study meets a pre-defined stopping criterion, the study will be paused, and data reviewed by the DMC prior to re-starting the enrollment.

The schedule of events is in Section 9.1, further details available in the study protocol.

2.2. Sample Size and Power

The sample size is not driven by statistical assumptions for formal hypothesis testing but was based on the safety objective for the study. A total of 200 subjects should provide sufficient information to assess safety and immunogenicity.

The sample size will also be adequate to establish variance of immune response in this target population and plan future studies.

2.3. Randomization Methodology

A total of 200 subjects are planned to be randomized in a 1:1:1:1 allocation ratio i.e. 50 subjects in each VAX-24 dose arm and 50 in the PCV20 group. There will be no stratification factors.

Treatment will be assigned automatically by the IBM EDC (Electronic Data Capture) system during the study, using a Randomization List generated and uploaded before the enrollment of the first subject.

2.4. Stopping Rules

During the vaccination period(s), if any of the stopping rules are triggered, no further administration of study vaccine(s) will occur until safety data are reviewed by the DMC in communication with the Medical Director and the Investigator at the site where the event

occurred, as needed. Study dosing may be resumed if the DMC determines it is safe to proceed with no modifications or with modifications to the protocol plans.

[REDACTED]

Enrollment may be resumed following review of available safety data by the DMC. Vaxcyte clinical safety team will refer to the VAX24-102 Safety Medical Monitoring Plan for detailed procedures on stopping rule reporting and safety oversight for the study.

The study is planned to be completed after all subjects have completed the Month 6 visit (or Early Discontinuation, as appropriate), all necessary safety follow-up has been completed, and all data have been monitored and queries have been resolved. The Sponsor reserves the right to terminate the study prior to the planned study completion.

2.5. Blinding

This is an observer-blind study in which all participants, Investigators, and study personnel involved in the conduct of the study, including data management, are blinded to treatment assignment except for:

- Unblinded independent statisticians who will prepare and have access to the randomization code
- Third-Party Vendors (Supply Management)
- Unblinded pharmacist or designee at site who will prepare Investigational Product (IP)
- Unblinded Administrator at site who will dispense IP
- Unblinded Clinical Research Associate/Study Monitor who will monitor pharmacy
- Unblinded Lead Clinical Research Associate and Clinical Trial Assistant who will review the unblinded Clinical Research Associate/Study Monitor's reports and manage IP supply orders and inventory
- Unblinded Sponsor Quality Assurance (QA) Consultant(s)

Although unblinded to treatment assignment, none of the above roles will have access to unblinded summaries of immunogenicity or safety data.

The following personnel will have access to unblinded data, including individual treatment assignment and individual immunogenicity data, in order to discharge their roles for data analysis and review during the conduct of the study:

- The unblinded statistical programming team, the unblinded data manager, and independent support statistician who will prepare Safety unblinded reports for DMC meetings (excluding immunogenicity data)
- The DMC members who will review Safety unblinded data reports (excluding immunogenicity data)
- The unblinded programming team and the unblinded statistician who will prepare the unblinded report for the Final Analysis

Other than the above-mentioned personnel, all other individuals involved in the study conduct, statistical analysis and reporting will remain blinded to individual treatment assignments and individual immunogenicity data until official study unblinding at the end of the study.

2.6. Interim Analyses

No Interim Analysis is planned for this study.

2.7. Schedule of Analyses

Only one Final Analysis is planned for this study. The final database lock (DBL) will occur when all subjects have completed the study, and all data through the last Month 6 visit have been cleaned. Individual Treatment unblinding will be available to all study personnel after the final DBL. The Final Analysis will include all analyses described in this SAP. A single completed CSR will summarize safety findings through Month 6 and immunogenicity through Day 29 for all subjects.

3. STUDY ENDPOINTS

3.1. Efficacy Variables

No Efficacy endpoint has been defined for this study.

3.2. Safety Variables

Safety assessments performed during the study included solicited AE up to Day 8 and monitoring of unsolicited adverse events including NOCI and MAAE, physical examinations, measurement of vital signs.

The primary safety endpoints are:

- Percentage of subjects reporting solicited local reactions within 7 days after vaccination (redness, swelling, and pain at injection site).
- Percentage of subjects reporting solicited systemic events within 7 days after vaccination (fever, headache, fatigue, muscle pain, and joint pain).
- Percentage of subjects reporting unsolicited AEs within 1 month after vaccination.
- Percentage of subjects reporting SAEs within 6 months after vaccination.
- Percentage of subjects reporting NOCIs within 6 months after vaccination.
- Percentage of subjects reporting MAAEs within 6 months after vaccination.

3.3. Immunogenicity Variables

Immunogenicity samples will be collected for all subjects at Day 1, Day 29 and at the Early Discontinuation Visit for subjects discontinuing before Month 6 visit. Immunogenicity parameters to be determined include OPA and IgG assays.

The secondary endpoints related to Immunogenicity assessments are:

- 24 VAX-24 Pneumococcal serotype-specific OPA geometric mean titer (GMTs) at 1 month after vaccination (Day 29).
- 24 VAX-24 Pneumococcal serotype-specific IgG geometric mean concentration (GMCs) at 1 month after vaccination (Day 29).

[Redacted]

- [Redacted]
- █ [Redacted]
- █ [Redacted]
- █ [Redacted]

4. ANALYSIS SETS

4.1. Analysis Set Definitions

The following Analysis sets will be evaluated and used for presentation and analysis of the data:

- **Screened Population:** Includes all screened subjects who provided informed consent and were assigned a study subject number, regardless of whether the subject was randomized or not. This population will be used to account fully for subject disposition, starting with the informed consent. The screened population will not be analyzed as such but will be available in the clinical database.
- **Randomized Population:** Includes all subjects from the Screened Population who consented, provided demographic and other Baseline Screening measurements, and were randomized. Each subject will be analyzed as randomized.
- **Exposed Population:** Includes all subjects from the Screened Population who received at least one study vaccine administration. Each subject will be analyzed as treated.
- **Safety Population :** Includes all subjects in the Exposed Population but excluding subjects lost to follow up at Day 1 reporting no solicited or unsolicited AEs. Each subject will be analyzed as treated.
- **Immunogenicity Evaluable Population (IEP):** Includes all subjects in the Exposed Population who:
 - Had no major protocol deviation that would impact immunogenicity assessment or other reason to be excluded as defined prior to unblinding or analysis.
 - Had not received a prohibited medication or vaccine. Identification of subjects receiving prohibited medications will be done via a medical review from the Sponsor of a listing of all concomitant medications.
 - Provided evaluable serum sample results for baseline, the relevant post-vaccination time points, and within the required time frames:
 - Baseline: Day 1 or within 30 days before first study vaccine administration
 - Day 29: Day 26 through Day 34, inclusive

Each subject will be analyzed as treated. Programming identification of patients excluded of the IEP is detailed in Section 4.2.

“As randomized” means according to the vaccine regimen to which the subject was randomized, while “as treated” means according to the vaccine regimen a subject received, rather than the vaccine regimen to which the subject may have been randomized.

The Randomized Population will be used for the analysis of exposure.

The Safety Population will be the primary set for the analysis of the safety parameters.

The Immunogenicity Evaluable Population will be the primary set for the immunogenicity analysis, with the Exposed Population set as supportive.

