5.13 Prohibited Medications and Therapies

Subjects must not have received or be planning to receive:

- Licensed or investigational pneumococcal (pneumonia) vaccine.
- Investigational agents or study product from 30 days prior to Day 1 through the duration of the study.
- Other (non-pneumococcal) licensed vaccines from 30 days prior to Day 1 through Day 29.
- Blood or blood product (including IGIV) from 90 days prior to Day 1 through the duration of the study.
- Systemic immunosuppressant therapy (eg, chemotherapeutics) and immunostimulants.
- Immunomodulatory medications (eg, oral corticosteroids) from 30 days prior to Day 1 or received systemic corticosteroids exceeding physiologic replacement doses within 14 days prior to study vaccination through Day 29.

The history of all prohibited medications at any time during study participation (regardless of association with an AE) will be collected.

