9.3 Populations for Analysis

Randomized Population: All screened subjects who provide informed consent, provide demographics, other baseline and screening measurements, are randomized, and are assigned a study subject ID (number). Each subject will be analyzed as randomized (i.e., according to the vaccine regimen to which the subject was randomized).

Exposed Population: All subjects who receive the study vaccination.

Safety Population: All subjects in the Exposed Population who provide safety assessment data. This includes any subjects not lost to follow-up at Day 1, as they will be at risk for reporting an SAE. Each subject will be analyzed as treated (i.e., according to the vaccine regimen a subject received, rather than the vaccine regimen to which the subject may have been randomized).

Immunogenicity Evaluable Population (IEP): The immunogenicity population will be analyzed as treated (i.e., according to the vaccine regimen a subject receives, which may be different from the vaccine regimen to which the subject is randomized in the case of treatment errors).

The IEP includes all subjects in the Exposed Population who:

- Have no major protocol deviation that would impact immunogenicity assessment or other reason to be excluded as defined prior to unblinding or analysis.
- Have not received a prohibited medication or vaccine.
- Provide evaluable serum sample results for baseline, the relevant post-vaccination time points, and within the required time frames:
 - Baseline: Day 1 or within 30 days before first study vaccine administration
 - Day 29: Day 26 through Day 34, inclusive

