4.2. Protocol Deviations

All deviations from the protocol are documented in the study file. In addition, deviations are reported to the Institutional Review Board as applicable.

Subject-specific deviations are recorded in the subject's source documents. The Sponsor will review all protocol deviations (PDs) on an ongoing basis and will be responsible for categorizing protocol deviations as exclusionary from IEP. At the time of Final DBL, [REDACTED] will download the 'dv' csv file from IBM including all deviations entered in the system and will send it to the Sponsor. The Sponsor will use this source data to produce a classification Excel file by adding 2 new columns:

- IEPEXCL ("Leads to Exclusion from IEP?"). This column will be filled for each PD with:
 - o 'Yes' if the PD leads to exclusion of the subject from the IEP
 - o 'No' if the PD does not lead to exclusion of the subject from the IEP
- IEPEXCLREAS ("Reason for leading to exclusion from IEP"). This column will be filled for each row where IEPEXCL=Yes, with some categorical reasons of exclusions. It is expected that prohibited medication/vaccine, immunogenicity samples taken out of window, and other major PDs will be recorded as PD and classified as exclusionary from IEP by the Sponsor.

The PD classification file will be finalized prior to the final DBL. All PDs and their classification will be presented in a data listing.

In addition of the PD classification by the Sponsor, out of window immunogenicity samples will be identified programmatically, and corresponding subjects will be excluded from the IEP, even if there was not an associated exclusionary PD.

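### The immunogenicity evaluable set excludes subjects for prohibited products received after their Day 29 serum was drawn; the cost is small and the fix is a wording change

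*SAP*

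**What the plan says.** The IEP is the primary set for immunogenicity, with the Exposed Population as supportive (SAP 4.1).

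- **Prohibited-product criterion.** SAP 4.1: "Had not received a prohibited medication or vaccine". Protocol 9.3: "Have not received a prohibited medication or vaccine". Neither gives a time limit. SAP 4.1 adds that recipients are identified by a Sponsor medical review of a listing of all concomitant medications.
- **Deviation criterion.** The SAP 4.1 item just before it reads "Had no major protocol deviation that would impact immunogenicity assessment or other reason to be excluded as defined prior to unblinding or analysis". It is limited to deviations that matter for the assay result; the prohibited-product item has no such limit.
- **Classification.** For each deviation the Sponsor enters Yes or No in the column IEPEXCL. SAP 4.2 states the expectation that "prohibited medication/vaccine, immunogenicity samples taken out of window, and other major PDs will be recorded as PD and classified as exclusionary from IEP".
- **Windows.** Protocol 5.13 lists six classes. Two run to the end of the study: "Investigational agents or study product from 30 days prior to Day 1 through the duration of the study" and "Blood or blood product (including IGIV) from 90 days prior to Day 1 through the duration of the study". Two carry no dates: "Licensed or investigational pneumococcal (pneumonia) vaccine" and "Systemic immunosuppressant therapy (eg, chemotherapeutics) and immunostimulants". Two end at Day 29: other licensed vaccines and, on its most natural reading, the immunomodulator and corticosteroid item.
- **Collection.** Protocol 5.13 collects prohibited use throughout participation, and protocol 6.1.5 includes it in the Month 3 and Month 6 calls.

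**The concern.** For a subject in the IEP, the last scheduled serum sample is the Day 29 draw, accepted from Day 26 through Day 34. Safety follow-up then continues to Month 6. A product received in those later months cannot change a titre already fixed in the tube. The criterion as written still removes the subject, so membership of the primary immunogenicity set depends on events after the outcome was measured. What is at stake is some precision in the geometric mean ratios and response proportions, and a primary set that discards sound results.

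**Working it through.** **Step 1. Which classes reach past the draw (protocol 5.13)?**

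| Class | Stated end | Reach past the Day 29 draw |
|---|---|---|
| Investigational agents | End of study | Explicit |
| Blood products | End of study | Explicit |
| Pneumococcal vaccine | None stated | Plain reading, by inference |
| Immunosuppressants, immunostimulants | None stated | Plain reading, by inference |
| Other licensed vaccines | Day 29 | Depends on the meaning of Day 29 |
| Immunomodulators, corticosteroids | Day 29 (most natural reading) | Depends on the meaning of Day 29 |

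Two classes are explicit and two more are inferred. For the last two the documents do not settle the matter. If Day 29 is the calendar day, a subject drawn on Day 26, 27 or 28 has 29 − 26 = 3, 2 or 1 days left in which a later product would still exclude. If it is the Day 29 visit, where protocol 9.2 and SAP 5.2 end the treatment period, those days disappear. The same ambiguity decides whether a product received after Day 29 but before a Day 30–34 draw is prohibited at all.

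**Step 2. Would the plan find and exclude these subjects?** Use is collected to Month 6, the listing under review is not cut at the draw, and SAP 4.2 expects exclusion. By default, yes.

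**Step 3. Size.** The plan's own figure is 200 subjects at 1:1:1:1, and 200/4 = 50 per arm, which agrees with SAP 2.3. There is no power calculation to reproduce: protocol 9.1 and SAP 2.2 say the sample size was not driven by hypothesis testing.

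Inputs: N = 200; 4 arms; about 20 sites (protocol synopsis); the ANOVA with arm and site as fixed effects (SAP 6.5.1), hence 4 + 20 − 1 = 23 parameters; two-sided 0.05. Assumptions: the number of subjects lost, k, and a log10 SD of 0.6 (needed only for the interval factor). Imbalance of arms within sites is ignored.

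Half-width on the log10 scale = t(0.975, N − 23) × SD × √(1/nA + 1/nB).

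With no loss: t(177) = 1.97346, and the half-width is 1.97346 × 0.6 × √(2/50) = 0.2368. The interval is the estimated ratio multiplied and divided by 10^0.2368 = 1.725.

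Losses spread evenly over arms:

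| k of 200 | df | n per arm | Widening | Interval factor |
|---|---|---|---|---|
| 1 (0.5%) | 176 | 49.75 | 0.25% | 1.728 |
| 2 (1%) | 175 | 49.5 | 0.51% | 1.730 |
| 4 (2%) | 173 | 49 | 1.03% | 1.735 |
| 10 (5%) | 167 | 47.5 | 2.64% | 1.750 |

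All losses in one of the two compared arms (nA = 50 − k, nB = 50): k = 1 gives 0.51%, k = 2 gives 1.04%, k = 4 gives 2.17%.

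As a cross-check without the degrees-of-freedom term, √(50/49) − 1 = 1.0% for one lost per arm (4 in total), which agrees with the table. At 5 lost per arm (20 in total), √(50/45) − 1 = 5.4%.

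**The case against.** The strongest reply is that the text does not force exclusion. SAP 4.1 sends identification to a medical review, SAP 4.2 lets the Sponsor enter No, and it only expects prohibited use to be exclusionary. It also groups such use with other major deviations, which the preceding criterion limits to those that affect the immunogenicity assessment. This softens the default but does not replace it: the prohibited-product item stands as a separate requirement, and no written criterion supports keeping a subject who fails it.

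A second reply is that treatment begun soon after the draw may mark a condition already present at vaccination, so a rigid date rule could override useful judgement. That stands, and the fix keeps medical review for this reason.

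A third is that excluding every recipient is simple, conservative and prespecified, with an all-exposed analysis in support. That is fair and is why the point is minor, but the Exposed Population is only supportive.

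Three stronger readings are tempting and not supported:
- That four classes expressly run to Month 6. Only two do. The introductory wording of protocol 5.13 resembles eligibility language, so the reach of the two undated classes is an inference.
- That a draw on Day 26–28 certainly exposes a subject to exclusion for a later Day 29-limited product, or that receipt on Days 30–34 before a late draw is certainly permitted. Each needs the calendar-day reading.
- That the rule biases the comparison of arms. Nothing in the documents suggests post-draw use differs by arm, and classification is finalised before the final lock, with general unblinding after it.

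**Conclusion.** The point holds and is minor. The stated default removes valid Day 1 and Day 29 results from the primary immunogenicity set for receipt after the draw: explicitly for two of the six classes, on a plain reading for two more, and undetermined for the remaining two.

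The loss is one of precision only: about 0.25% of interval width per subject if losses are spread over arms, about 0.5% if the subject is in a compared arm. The percentage widening rests on 200 subjects and about 20 sites; the interval factors also need the assumed SD. Calling the total small rests on an assumed low rate, because the documents give none; the exclusions for poor health, immunosuppression and recent malignancy point that way. No changed conclusion is shown, and the Exposed Population analyses and listings retain the data.

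**What to change.** 1. **SAP 4.1:** limit the prohibited-product criterion to products received on or before the subject's own Day 29 immunogenicity draw.
2. **SAP 4.2:** make No the default for IEPEXCL when the only prohibited product came after that draw, still subject to blinded medical review under the separate major-deviation criterion.
3. **Unclear dates:** treat a receipt date that cannot be placed before or after the draw as before it, so exclusion still applies; a partial date that can only fall after the draw counts as after. A rule is needed because SAP 6.2.3 only sorts undetermined dates into concomitant use and SAP 6.1.6 imputes no medication dates.
4. **SAP 7:** record this as a change from protocol 9.3 before unblinding.
5. **Protocol 5.13:** the sponsor should reconcile whether Day 29 there means the calendar day or the visit. Until then, any statement about early or late draws for the Day 29-limited classes is conditional.

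The prohibited products and their windows are not changed. Apart from the clarification in item 5, the edits are to the SAP alone. The cost is a little extra date checking and a documented departure from protocol 9.3; no new data are needed.

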4.2. Protocol Deviations

All deviations from the protocol are documented in the study file. In addition, deviations are reported to the Institutional Review Board as applicable.

Subject-specific deviations are recorded in the subject's source documents. The Sponsor will review all protocol deviations (PDs) on an ongoing basis and will be responsible for categorizing protocol deviations as exclusionary from IEP. At the time of Final DBL, [REDACTED] will download the 'dv' csv file from IBM including all deviations entered in the system and will send it to the Sponsor. The Sponsor will use this source data to produce a classification Excel file by adding 2 new columns:

- IEPEXCL ("Leads to Exclusion from IEP?"). This column will be filled for each PD with:
 - o 'Yes' if the PD leads to exclusion of the subject from the IEP
 - o 'No' if the PD does not lead to exclusion of the subject from the IEP
- IEPEXCLREAS ("Reason for leading to exclusion from IEP"). This column will be filled for each row where IEPEXCL=Yes, with some categorical reasons of exclusions. It is expected that prohibited medication/vaccine, immunogenicity samples taken out of window, and other major PDs will be recorded as PD and classified as exclusionary from IEP by the Sponsor.

The PD classification file will be finalized prior to the final DBL. All PDs and their classification will be presented in a data listing.

In addition of the PD classification by the Sponsor, out of window immunogenicity samples will be identified programmatically, and corresponding subjects will be excluded from the IEP, even if there was not an associated exclusionary PD.

